5.5.12.1.2. Suicide-Related Thoughts and Behaviors

Suicidal ideation, suicidal behavior, and self-injurious behavior without suicidal intent occurring during treatment, based on the Columbia-Suicide Severity Rating Scale (C-SSRS), will be summarized by treatment (SP III, SP IV separately). In particular, for each of the following events, the number and percent of patients with the event will be enumerated by treatment: completed suicide, nonfatal suicide attempt, interrupted attempt, aborted attempt, preparatory acts or behavior, active suicidal ideation with specific plan and intent, active suicidal ideation with some intent to act without specific plan, active suicidal ideation with any methods (no plan) without intent to act, nonspecific active suicidal thoughts, wish to be dead, and self-injurious behavior without suicidal intent.

In addition, the number and percent of patients who experienced at least one of various composite measures during Study Period III and Study Period IV separately will be presented and compared. Composite measures include followings:

- suicidal behavior (completed suicide, non-fatal suicidal attempts, interrupted attempts, aborted attempts, and preparatory acts or behavior),
- suicidal ideation (active suicidal ideation with specific plan and intent, active suicidal ideation with some intent to act without specific plan, active suicidal ideation with any methods [no plan] without intent to act, non-specific active suicidal thoughts, and wish to be dead)
- suicidal ideation or behavior.

The number and percent of patients who experienced at least 1 of various comparative measures during treatment will be presented and compared for Study Period III and summarized for Study Period IV. Comparative measures include followings:

- TE suicidal ideation (1-5) compared to recent history,
- TE suicidal ideation (1-5) compared to all prior history,
- TE serious suicidal ideation (0-3 to 4-5) compared to recent history,
- TE serious suicidal ideation (0-3 to 4-5) compared to all prior history,
- Emergence of serious suicidal ideation (0 to 4-5) compared to recent history
- Emergence of serious suicidal ideation (0 to 4-5) compared to all prior history
- Improvement in suicidal ideation at endpoint compared to baseline,
- Emergence of suicidal behavior (6-10) compared to all prior history.

Specifically, the following outcomes are C-SSRS categories and have binary responses (yes/no). The categories have been re-ordered from the actual scale to facilitate the definitions of the composite and comparative endpoints, and to enable clarity in the presentation of the results.

Category 1 – Wish to be Dead

Category 2 – Non-specific Active Suicidal Thoughts

Category 3 – Active Suicidal Ideation with Any Methods (Not Plan) without Intent to Act

Category 4 – Active Suicidal Ideation with Some Intent to Act, without Specific Plan

Category 5 – Active Suicidal Ideation with Specific Plan and Intent

Category 6 – Preparatory Acts or Behavior

Category 7 – Aborted Attempt

Category 8 – Interrupted Attempt

Category 9 – Actual Attempt (non-fatal)

Category 10 – Completed Suicide

Self-injurious behavior without suicidal intent is also a C-SSRS outcome (although not suicide-related) and has a binary response (yes/no).

Composite endpoints based on the above categories are defined below.

- Suicidal ideation: A “yes” answer at any time during treatment to any 1 of the 5 suicidal ideation questions (Categories 1-5) on the C-SSRS.
- Suicidal behavior: A “yes” answer at any time during treatment to any 1 of the 5 suicidal behavior questions (Categories 6-10) on the C-SSRS.
- Suicidal ideation or behavior: A “yes” answer at any time during treatment to any 1 of the 10 suicidal ideation and behavior questions (Categories 1-10) on the C-SSRS.

The following outcome is a numerical score derived from the C-SSRS categories. The score is created at each assessment for each patient and is used for determining treatment emergence.

- Suicidal Ideation Score: The maximum suicidal ideation category (1-5 on the C-SSRS) present at the assessment. Assign a score of 0 if no ideation is present.

For Study Period III and Study Period IV, comparative endpoints of interest are defined below. “Treatment emergence” is used for outcomes that include events that first emerge or worsen. “Emergence” is used for outcomes that include events that first emerge.

- Treatment emergent suicidal ideation compared to recent history:
An increase in the maximum suicidal ideation score during treatment (Visits 3.01 to 16 for Study Period III; Visits 16.01 to 18 for Study Period IV) from the maximum suicidal ideation category during the screening and lead-in periods (EM patients: C-SSRS scales taken at CGAP Visit 3 for Study Period III; CM patients: C-SSRS scales taken at CGAP Visits 1 to 3 excluding “lifetime” for Study Period III; EM patients: C-SSRS scales taken at CGAP Visits 3 to 16 for Study Period IV, CM patients: C-SSRS scales taken at Visits 1 to 16 excluding “lifetime” for Study Period IV). Recent history excludes “lifetime” scores from the Baseline C-SSRS scale or Baseline/Screening C-SSRS scale.
- Treatment emergent suicidal ideation compared to all prior history:
- The same definition above except the baseline includes “lifetime” scores. See [Table CGAP. 5.4](#) for more detail.
- Treatment emergent serious suicidal ideation compared to recent history:
An increase in the maximum suicidal ideation score to 4 or 5 on the C-SSRS during treatment (Visits 3.01 to 16 for Study Period III; Visits 16.01 to 18 for Study Period IV) from not having serious suicidal ideation (scores of 0-3) during the screening and lead-in periods (EM patients: C-SSRS scales taken at CGAP Visit 3 for Study Period III, CM patients: C-SSRS scales taken at CGAP Visits 1 to 3 excluding “lifetime” for Study Period III; EM patients: C-SSRS scales taken at CGAP Visits 3 to 16 for Study Period IV, CM patients: C-SSRS scales taken at Visits 1 to 16 excluding “lifetime” for Study Period IV). Recent history excludes “lifetime” scores from the Baseline C-SSRS scale or Baseline/Screening C-SSRS scale.

- Treatment emergent serious suicidal ideation compared to all prior history:
- The same definition above except the baseline includes “lifetime” scores. See [Table CGAP. 5.4](#) for more detail.
- Emergence of serious suicidal ideation compared to recent history:
An increase in the maximum suicidal ideation score to 4 or 5 on the C-SSRS during treatment (Visits 3.01 to 16 for Study Period III; Visits 16.01 to 18 for Study Period IV) from no suicidal ideation (scores of 0) during the screening and lead-in periods (EM patients: C-SSRS scales taken at CGAP Visit 3 for Study Period III, CM patients: C-SSRS scales taken at CGAP Visits 1 to 3 excluding “lifetime” for Study Period III; EM patients: C-SSRS scales taken at CGAP Visits 3 to 16 for Study Period IV, CM patients: C-SSRS scales taken at Visits 1 to 16 excluding “lifetime” for Study Period IV). Recent history excludes “lifetime” scores from the Baseline C-SSRS scale or Baseline/Screening C-SSRS scale.
- Improvement in suicidal ideation at endpoint compared to baseline:
A decrease in suicidal ideation score at endpoint (the last measurement during treatment; Visits 3.01 to 16 for Study Period III; the last measurement during open-label phase Visits 16.01 to 18 for Study Period IV) from the baseline measurement (EM patients: CGAP Visit 3 for Study Period III, CM patients: the last non missing measure during CGAP Visit 1 to 3 for Study Period III; Both EM and CM patients: the last non-missing measure during Visits 3.01 to 16 for Study Period IV).
- Emergence of suicidal behavior compared to all prior history:
The occurrence of suicidal behavior (Categories 6-10) during treatment (Visits 3.01-16 for Study Period III; Visits 16.01 to 18 for Study Period IV) from not having suicidal behavior (Categories 6-10) prior to treatment (EM patients: All CGAN Visits 1-12 including “lifetime” for Study Period III, all CGAN Visits 1-12 including “lifetime” and All CGAP Visits 3.01-16 for Study Period IV. CM patients: All CGAP Visits 1-3 including “lifetime” for Study Period III, All CGAP Visits 1 to 16 including “lifetime” for Study Period IV).

Patients who discontinued from the study with no post-baseline C-SSRS value will be considered unevaluable for analyses of suicide-related events. Only evaluable patients will be considered in the analyses

Listing of Subjects with Suicidal Ideation, Behavior, or Self-injurious Behavior at Any Time Post-Baseline will be created.

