For safety analysis, when statistical model is used such as MMRM, or ANCOVA, then 4 arms (EM120, EM240, CM120, CM240) will be used without any statistical comparisons between arms.

For listings, they will be displayed by 6 arms (LY120/LY120, LY240/LY240, PLA/LY120, PLA/LY240, CM120, CM240), unless otherwise specified.

All statistical tests will be conducted at a 2-sided alpha level of 0.05, and 95% confidence intervals will be provided, if appropriate. No adjustments for multiplicity will be applied to any safety or effectiveness analyses.

Change from baseline of continuous variables with repeated measures will be analyzed using a mixed model repeated measures (MMRM) analysis, unless otherwise specified. An MMRM analysis refers to a restricted maximum likelihood (REML)-based, mixed-effects repeated measures analysis using all the longitudinal observations at each post-baseline visit.

For other continuous variables without repeated measures, the change from baseline to LOCF endpoint will be analyzed using an analysis of variance (ANOVA) or ANCOVA model.

Unless otherwise specified, when an ANOVA model or ANCOVA model is used to analyze a continuous efficacy variable, type III sum-of-squares for the least-squares means (LSMean) will be used for the statistical comparisons.

Visit-wise binary efficacy variables will be analyzed using a generalized linear mixed model (GLIMMIX) as pseudo-likelihood-based mixed effects repeated measures analysis for categorical data (MMRM-CAT).

For categorical efficacy variables without repeated measures, comparisons between treatment groups will be performed using logistic regressions.

For other categorical variables without repeated measures, comparisons between treatment groups will be performed using Fisher's exact tests unless otherwise specified. For example,

- Baseline patient characteristics
- Safety measures (including percentages of patients with TEAEs, SAEs, and AEs reported as a reason for discontinuation, as well as those patients who met categorical criteria for changes in vital signs and weight, ECGs, and laboratory tests)

Only scheduled visit data will be available for the following data. In other words, there will be no unscheduled visit data;

- Patient migraine headache data collected by diary
- PGI-S
- PGI-I
- MSQ v2.1
- MIDAS
- PSMQ-M
- HCRU

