5.5.1.4. Baseline and Post-Baseline Definition

[Table CGAP. 5.4](#) describes the rules for determining the patient population and baseline and post-baseline observations for each study phase and type of analysis. When “last of Visit x-x” is used in the table, the last nonmissing observation obtained in the visit interval will be used.

Table CGAP. 5.4 Patient Population with Baseline and Post-Baseline Definitions by Study Period and Type of Analysis

Study Period/Analysis	Patient Population	Baseline Observation	Post-baseline Observation(s)
Study Period III			
Efficacy analyses	ITT Population with a baseline and at least 1 post-baseline observation	Visit 3	All Visits 3.01–16
Mean change from baseline in the number of migraine headache days	PPS Population with a baseline and at least 1 post-baseline observation	Visit 3	All Visits 3.01–16
Quality of Life analyses	ITT Population with a baseline and at least 1 post-baseline observation	Visit 3	All Visits 3.01–16
TEAEs	Safety Population	EM: CGAN Visit 1 – CGAP Visit 3 CM: All Visits 1–3. Pre-existing condition that is still ongoing at Visit 1 should be evaluated as baseline values.	All Visits 3.01–16
Serious Adverse Events, Discontinuations due to Adverse Events	Safety Population	NA	All Visits 3.01–16
C-SSRS categorical analyses	Safety population with a baseline and at least 1 post-baseline C-SSRS assessment	EM: Recent History: CGAP Visit 3 All Prior History: All CGAN Visits 1-12 including lifetime ^a CM: Recent History: All CGAP Visits 1–3 excluding lifetime ^a	All Visits 3.01–16

Study Period/Analysis	Patient Population	Baseline Observation	Post-baseline Observation(s)
		All Prior History: All CGAP Visits 1 – 3 including lifetime ^a	
C-SSRS categorical analyses for improvement	Safety population with a baseline and at least 1 post-baseline C-SSRS assessment	EM: Visit 3 CM: Last of CGAP Visit 1-3.	Last of 3.01–16
Treatment emergent abnormal laboratory values	Safety Population with normal laboratory values at all nonmissing baseline visits (with respect to direction being analyzed) and who have at least 1 post-baseline observation	EM: Visit 3 CM: All Visits 1–3	All Visits 3.01–16
Treatment emergent immunogenicity	Safety Population. ADA follow-up cohort (See Section 5.5.12.1.6)	EM (LY120/LY120, LY240/LY240): CGAN Visit 3 EM (PLA/LY120, PLA/LY240): CGAP Visit 3 CM: Visit 3	All Visits 3.01–16

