		from Visits 3–16 CM: Low: Minimum value from Visits 1–16 High: Maximum value from Visits 1–16	
C-SSRS categorical analyses	Post-treatment Population with a baseline and at least 1 post-baseline C-SSRS assessment	EM: Recent History: CGAP Visit 3-16 All Prior History: All CGAN Visits 1-12 including lifetime ^a and All CGAP Visits 3.01-16 CM: Recent History: All CGAP Visits 1–16 excluding lifetime ^a All Prior History: All CGAP Visits 1-16 including lifetime ^a	All Visits 16.01–18
C-SSRS categorical analyses for improvement	Post-treatment Population with a baseline and at least 1 post-baseline C-SSRS assessment	EM: Last of CGAP Visits 3.01-16 CM: Last of CGAP Visits 3.01-16	Last of 16.01–18

Abbreviations: ADA = Anti-Drug Antibody; CM = chronic migraine; C-SSRS = Columbia Suicide Severity Rating Scale; EM = episodic migraine; FEAE = follow-up emergent adverse event; ITT = intent-to-treat; PPS = per protocol set; TEAE = treatment emergent adverse event.

Note: Visit 3.01 indicates the first unscheduled visit occurring after Visit 3 and prior to Visit 4. Other visits can be interpreted in a similar manner. For example, Visit 12.01 indicates the first unscheduled visit occurring after Visit 12 and prior to Visit 13. For efficacy and quality of life measures without unscheduled visits data point, Visit 3.01 indicates scheduled collection visits after visit 3.

^a Lifetime is captured in the C-SSRS visit 1 CRF (EM: CGAN visit 1, CM: CGAP visit 1).

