5.5.12.1. Categorical Safety Variables

Unless specified otherwise, the categorical safety analyses will include both scheduled and unscheduled visits. Unless otherwise specified, categorical safety analyses will only be conducted for Study Period III and Study Period IV separately.

Comparisons between treatment groups for all categorical safety measures will be made using the Fisher's exact test for Study Period III with the safety population, unless otherwise specified.

Descriptive statistics only will be presented for the treatment groups in Study Period IV with the post-treatment population.

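### The C-SSRS improvement percentage keeps patients with a baseline ideation score of 0 in its denominator, so it is capped at the baseline prevalence of ideation and can differ between arms through baseline differences alone

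*SAP*

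**What the plan says.** SAP section 5.5.12.1.2 derives an ideation score at each C-SSRS assessment as the highest ideation category present (1 to 5), with the instruction "Assign a score of 0 if no ideation is present". Improvement is "A decrease in suicidal ideation score at endpoint", where endpoint is the last measurement of the period, compared with the baseline measurement. For Study Period III the baseline is CGAP Visit 3 for episodic-migraine (EM) patients and the last non-missing value from Visits 1 to 3 for chronic-migraine (CM) patients. For Study Period IV it is the last value from Visits 3.01 to 16 for both groups.

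Table CGAP. 5.4 (section 5.5.1.4) has separate rows for the improvement analysis. The population is "Safety population with a baseline and at least 1 post-baseline C-SSRS assessment" for Study Period III and "Post-treatment Population with a baseline and at least 1 post-baseline C-SSRS assessment" for Study Period IV. The only further exclusion in 5.5.12.1.2 is this: "Patients who discontinued from the study with no post-baseline C-SSRS value will be considered unevaluable for analyses of suicide-related events". None of these places requires a baseline score of at least 1.

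The comparative C-SSRS measures, improvement among them, are given as number and percent and are "presented and compared for Study Period III and summarized for Study Period IV". Section 5.5.12.1 supplies the method for Study Period III: "Comparisons between treatment groups for all categorical safety measures will be made using" Fisher's exact test. Section 5.5.1 adds "All statistical tests will be conducted at a 2-sided alpha level of 0.05", and the contrasts are EM120 vs EM240 and CM120 vs CM240.

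**The concern.** A proportion improved is informative when everyone in the denominator could improve. Here the denominator also holds patients at the floor of the score, who cannot. The percentage then depends on two things: how many patients had ideation at baseline, and how many of those got better. A reader of the table cannot separate them.

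Two consequences follow. The level of the percentage says little about improvement among patients with ideation. And two arms in which the same share of affected patients improve can show different percentages because they started with different numbers of affected patients. The second matters most for the EM arms. Their Study Period III baseline is the end of treatment in Study CGAN, after different prior exposure, so randomization at CGAN Visit 3 does not by itself balance ideation at this baseline.

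The described outputs do not let the reader repair this. The baseline characteristics in 5.5.4 do not include the C-SSRS. The planned C-SSRS listing covers ideation at any time after baseline, so a patient with ideation at baseline and none afterwards, the clearest improver, need not appear in it.

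**Working it through.** The SAP states no rate, power or sample size for this measure, so there is no figure to reproduce.

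**Inputs from the documents**
- Score floor of 0, and improvement as a decrease: SAP 5.5.12.1.2.
- Denominator: baseline plus at least one post-baseline C-SSRS, Table CGAP. 5.4.
- Planned patients per arm: 120 EM and 30 CM, SAP 5.2.1 and 5.2.2. The evaluable number will be no larger than the number treated.

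**Input assumed**
- Baseline prevalence of a score of at least 1: not given. The range 1% to 20% is used for illustration.

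**Step 1: identity.** Let N be the evaluable patients in an arm, k those with a baseline score of at least 1, and m those of the k who improve. Patients at 0 contribute nothing to m, so

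reported % = 100 × m/N = 100 × (k/N) × (m/k).

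Because m ≤ k, the reported percentage is at most 100 × k/N, the baseline prevalence.

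**Step 2: the ceiling (all k improve).**

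| Arm | k | Ceiling |
|---|---|---|
| EM, N = 120 | 1 | 1/120 = 0.8% |
| | 2 | 2/120 = 1.7% |
| | 6 | 6/120 = 5.0% |
| | 12 | 12/120 = 10% |
| | 24 | 24/120 = 20% |
| CM, N = 30 | 1 | 1/30 = 3.3% |
| | 2 | 2/30 = 6.7% |
| | 3 | 3/30 = 10% |
| | 6 | 6/30 = 20% |

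If half of the affected patients improve, each value is halved. With the denominator restricted to k, the result is m/k: 0%, 50% or 100% when none, half or all improve, whatever the prevalence.

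**Step 3: baseline difference alone.** Take two EM arms with 8 and 2 affected patients (assumed), half improving in each. The planned percentages are 4/120 = 3.3% and 1/120 = 0.8%. The restricted ones are 4/8 and 1/2, both 50%. Fisher's test on the planned table gives p = 0.37, so this is a distorted description and not a false positive.

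**Step 4: effect on the planned test.** Take the most extreme split: k affected patients in each arm, all improving in one arm and none in the other. Two-sided Fisher p-values:

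| k per arm | Planned, EM | Planned, CM | Restricted to k |
|---|---|---|---|
| 2 | 0.498 | 0.492 | 0.333 |
| 3 | 0.247 | 0.237 | 0.100 |
| 4 | 0.122 | 0.112 | 0.029 |
| 6 | 0.029 | 0.024 | 0.002 |

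Patients who cannot improve dilute the contrast. With 2 or 3 affected patients per arm, neither denominator can reach 0.05.

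**Step 5: comparison with the rest of the SAP.** Treatment-emergent low and high laboratory values (5.5.12.1.5) and ECG values (5.5.12.1.4) are analysed only in patients without that abnormality at baseline. Responder analyses (5.4.1) exclude patients with zero baseline migraine headache days. The improvement measure has no such condition, and no reason is given.

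**The case against.** The strongest objection is that little depends on this item. Counts are shown beside percentages, so the number who improved is visible. Treatment-emergent ideation, serious ideation, emergent behavior, the composite measures and the post-baseline listing carry the harm signal. If only one or two patients per arm have baseline ideation, the restricted percentage can take only a few values and a test is uninformative with either denominator. All of this stands and sets the severity. It does not give the reader the missing number, which is how many patients per arm could have improved.

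It can also be said that the population wording in Table CGAP. 5.4 is generic and is narrowed elsewhere. The row for vital signs, weight and ECGs has similar wording, and 5.5.12.1.4 then restricts the ECG low and high analyses to patients at risk. For improvement, however, 5.5.12.1.2 adds no restriction.

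The same argument does protect the emergence measures. A reader might infer that treatment-emergent serious ideation and emergence of serious ideation have a mirror-image fault, because patients already above the starting range stay in the denominator. The documents do not establish this: the definitions start from scores of 0-3 and of 0, which can be read as at-risk conditions. The effect would also be trivial at low prevalence. Removing 2 of 30 CM patients changes 1/30 = 3.3% to 1/28 = 3.6%; removing 4 of 120 EM patients changes 1/120 = 0.83% to 1/116 = 0.86%.

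**Conclusion.** The point holds as a minor improvement. As planned, the improvement percentage equals baseline prevalence times the proportion of affected patients who improve. It cannot exceed the prevalence, and the Study Period III comparison can shift through baseline differences alone. This follows from the SAP's own definitions. Only the size needs an assumption: a prevalence of 1% to 20% caps the result at about 1% to 20%, even if every affected patient improves.

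Two stronger readings are not supported. A reader might infer that the percentage must be near zero whatever happens. That requires low prevalence, which the documents do not give. Apart from clinician judgment of active suicidality, exclusion [29] in the protocol addendum names only ideation Questions 4 and 5 and suicidal behavior, within the past month. Scores of 1 to 3 are therefore not excluded as such. The addendum applies to CM patients only; the EM entry criteria are not in the supplied documents, and the Study Period IV baseline lies after treatment started. At 10% to 20% prevalence the result could lie anywhere from 0% to 10-20%. A reader might also infer that the measure reflects baseline ideation and not improvement. That is wrong: the numerator counts only patients who improved, and the percentage is 0 if nobody does.

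Suicidality by C-SSRS is listed among the other safety parameters under the primary objective, but no safety conclusion is shown to depend on this measure.

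**What to change.** In the two improvement rows of Table CGAP. 5.4 (Study Periods III and IV) and in the improvement definition in 5.5.12.1.2, restrict the population to patients with a baseline ideation score of at least 1 and at least one post-baseline C-SSRS. Use the baseline already defined for each period. Report n/N per arm descriptively and exempt this item from Fisher's exact test. N then tells the reader how many patients in each arm could have improved. Leave the emergence and treatment-emergent serious ideation denominators as they are.

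The cost is a population phrase, a sentence removing the test and a denominator flag in the program. No new data are needed. The downside is very small denominators, possibly zero in a CM arm, which is why counts should lead and percentages should not be over-read.
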